13.13 Confirmation of AEs

If an AE is reported by a subject at any time during medical interview, or at voluntary visit, or on telephone contact, information on the name of the AE, date and time of onset, severity, seriousness, causality, treatment, outcome, and date of outcome will be obtained and recorded. In the case of an SAE, the SAE should be reported in accordance with "14.10 Reporting of SAEs".

13.14 Confirmation of concomitant medication/therapy

Regarding concomitant medication, information on the name of the concomitant medication, route of administration, treatment duration, and reason for use of the concomitant medication will be recorded and entered in the eCRF. Regarding concomitant therapy, information on the name of the therapy, start and end dates of implementation, and reason for implementation will be recorded and entered in the eCRF.

14 AEs and adverse drug reactions (ADRs)

14.1 Definition of AE

An AE is any unfavorable or unintended sign (including abnormal laboratory changes), symptom, or disease occurring in an assigned subject from the start of study drug administration, whether or not related to the study drug. Events occurring before the start of study drug administration will be treated as a current medical condition in this study.

AEs required to be entered in the eCRF will be those occurring from the start of study drug administration to Day 14 in this study. SAEs related to the study drug should be collected until Day 28.

Moreover, the subject's current medical condition is not considered an AE unless the severity worsens or the incidence increases after study drug administration. If the investigators judge that the change in a laboratory test value is an unfavorable event for the subject, the event will be assessed as an AE.

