2 Observation and Examination Schedule

Item	Screening	Date of allocation	Observation period ⁵⁾												Discontinuation/ Exit Test ⁶⁾
			Day 0	Day 1	Day 2	Day 3	Day 4	Day 5	Day 6	Day 7	Day 8	Day 9	Day 10	Day 11 ~14	Day 15 ~28
Acceptable window	To Day 0	-2 days ⁷⁾	—	—	—	—	—	+1 day ⁷⁾	—	—	—	—	—	—	+1 day
Informed consent	●														
Medical history/current medical conditions	●														
Subject characteristics	●														
Height and weight	●														
Inclusion and exclusion criteria	●														
Percutaneous oxygen saturation (SpO2)	●														
Allocation		●													
Study drug administration ¹⁾			●	●	●	●	●	●	○	○	○	○	○		
7-point ordinal scale ²⁾			●	●	●	●	●	●	●	●	●	●	●	●	
Oxygen requirement			●	●	●	●	●	●	●	●	●	●	●	●	
Arterial blood gas analysis (PaO2, PaCO2, A-aDO2, others)			● ³⁾					●							●
Inflammatory markers, cytokines			● ³⁾		●		●								●
Chest HRCT or plain chest CT or Chest X-ray			●					●							●
Physical examination			●					●							●
Vital sign			●					●							●
12-lead ECG			●					●							●
Laboratory tests (blood chemistry, hematology and urinalysis)			●					●							●
Pregnancy test (urine or blood sample)			●												
adverse events ⁴⁾				●									●		
Concomitant medication/therapy		●	—									●			

● : Will be performed in all the subjects ○ : Will be performed only in the subjects who continue to receive the study drug after Day 5.

1) Inhalation administration will be started on the morning of Day 1 and performed twice daily (morning, evening) for 5 days, in principle (up to 10 days).

2) Will be evaluated every day during the period between Day 1 and Day 28. Use or no use of a ventilator will be included in this evaluation.

3) Will be performed prior to study drug administration.

4) Only the adverse events that have occurred until Day 14 after the start of study drug administration. may be collected and entered in the electronic case report form. Serious adverse events related to the study drug administration will be collected until Day 28.

- 5) Assessment of efficacy on the 7-point ordinal scale and oxygen requirement will be performed after completion of the second dose (inhalation) of the day.
- 6) Will be performed on the day of discontinuation if study drug administration has been prematurely discontinued before Day 5, or on the day of the last dose in the case that the last day is not Day 5.
- 7) Except 7-point ordinal scale and oxygen requirement.

3 Study Administrative Structure

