13.10 Arterial blood gas analysis (PaO₂, PaCO₂, A-aDO₂, others)

The subject will take a rest for at least 5 minutes under breathing of room air (when oxygen is being inhaled, the device will be temporarily removed) in a supine position on bed in a physicians room or in an examination room, then SpO₂ will be confirmed to be stable on a pulse oximeter and the blood sample will be collected from the artery using a blood collection kit designated by the medical institution. After blood sample is collected, the sample will be mixed adequately, and blood gas will be measured within 30 minutes using a blood gas analyzer. If it takes more than 10 minutes from blood collection to measurement, the blood sample will be kept in ice water. Whether the examination is possible or not will be determined to secure the subject safety considering the following criteria:

- (1) SpO₂ 94% or lower under the use of nasal high flow or mask
- (2) SpO₂ 93% or lower under oxygen supply of 4 L/min or more using nasal cannulas

A-aDO₂ will be automatically calculated using the following formula and automatically entered in the eCRF:

$$A-aDO_2 = (PB - PH_2O) \times FiO_2 - PaCO_2/R + \{PaCO_2 \times FiO_2 \times (1-R)/R\} - PaO_2$$

, where

PB: barometric pressure (measured at each medical institution)

PH₂O: partial pressure of water vapor in inspired air (47 mmHg)

R: respiratory quotient (0.80)

FiO₂: fraction of inspiratory oxygen (0.21)

The date of sample collection and the measurement values of PBs and PaO₂, PaCO₂, pH, SaO₂ will be entered in the eCRF

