14.8 Observation of AEs

The investigators shall observe the occurrence of AEs carefully through medical interview, medical examination, etc. from the start of study drug administration. If any AE is observed, appropriate measures should be taken, and the AE shall be followed up by the investigators until the AE disappears

or resolves as far as possible. However, if the investigators judge that further follow-up observation is not necessary and discontinue follow-up observation, or if the subject refuses it, the reason shall be entered in the eCRF.

For any AEs that have occurred, information of the name of the event, date and time of onset (or date and time when the event was found), severity, seriousness (serious/non-serious), action taken with the study drug (if yes, its contents), treatment for the event (yes or no), outcome, date and time of outcome (when the event disappeared, the date and time of disappearance), and causality to the study drug should be entered in detail in the eCRF.

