14.10 Reporting of SAEs

14.10.1 Principal investigator

If an SAE occurs during the period from the start of study drug administration to Day 14, the investigators will take the necessary measures with the highest priority given to the safety of the subject, regardless of whether it is related to the study drug or not. The principal investigator will report the event to the sponsor. However, if the event is an SAE and related to the study drug, the event that have occurred until Day 28 will be reported to the sponsor in the same manner even after completion of the above-mentioned period.

The procedures are outlined below.

- (1) The sponsor should be informed of the occurrence of an SAE within 24 hours of acknowledgment of the occurrence (A form of “Report on serious adverse event (initial announcement)” shall be used, whenever possible). In addition, the SAE should be immediately reported to the head of the medical institution.

- (2) A form of “Report on serious adverse event” shall be prepared and reported to the sponsor and the head of the medical institution at the earliest possible time within 7 days after the first announcement has been submitted to the sponsor, and a copy of the report will be retained.
- (3) The investigators shall make efforts to collect more detailed information, and report it to the sponsor and the head of the medical institution if new information becomes available.

Emergency Contact (Sponsor)

Nobel Pharma Co., Ltd. Research and Development Division [name] [contact]、[contact] Night and holiday : [REDACTED] [REDACTED]

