17.1.2 Safety population

All subjects who received the assigned study drug will be included in the Safety Population (SP).

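### Harm from the pre-dose Day 1 blood gas is not captured as an AE or reported as an SAE, because collection opens only at the first dose

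*Protocol*

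**What the plan says.** **When safety collection opens.** Protocol 14.1 defines an AE as an unfavourable sign, symptom or disease "occurring in an assigned subject from the start of study drug administration, whether or not related to the study drug". For anything earlier the rule is: "Events occurring before the start of study drug administration will be treated as a current medical condition in this study". One exception follows: a "current medical condition is not considered an AE unless the severity worsens or the incidence increases after study drug administration". Section 14.8 starts the observation of AEs at the same point. Section 14.10.1 opens the sponsor-reporting duty, with its 24-hour limit, in the same way: "If an SAE occurs during the period from the start of study drug administration to Day 14".

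**What is done before that.** Section 13 dates the study period from informed consent. In the Observation and Examination Schedule (section 2), footnote 3 says of the baseline blood gas: "Will be performed prior to study drug administration". Sections 5.2.1.2 and 5.2.1.6 place it on Day 1. Section 13.10 requires at least 5 minutes' rest on room air before the arterial sample, and "when oxygen is being inhaled, the device will be temporarily removed". The same section has the feasibility of the test judged for the subject's safety, against two criteria based on SpO₂ and oxygen support.

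**Who is sampled.** Inclusion criterion 2 (section 7.1) requires a room-air SpO₂ of 93% or less. Section 7 admits ordinal-scale Categories 3 to 5, which include patients on noninvasive ventilation or high-flow oxygen.

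**The concern.** The protocol schedules an invasive test on room air in hypoxaemic patients and itself treats the test as needing a safety judgement. Yet the first time each subject has it, the test falls in the gap between consent and first dose, where no AE can exist by definition. If a subject deteriorates during or just after this sampling, the written rule files the event as a condition the patient already had.

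What is at stake is oversight of the study's own procedure. The sponsor's duties in section 14.10.2 to follow up, to report to the authorities where required and to inform other sites are triggered by a reported SAE. Without that trigger, prompt learning that a mandated test is causing harm depends on someone noticing it in records kept for other purposes.

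**Working it through.** The plan gives no figure on this point, so the check is mainly one of reading sections against each other.

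**Step 1: follow one event through the rules.** Suppose a subject deteriorates because of the Day 1 pre-dose sampling.

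- *Never dosed.* Under 14.1 there is no AE, and under 14.10.1 no reportable SAE. The worsening exception cannot apply, because it refers to change after dosing. The subject is outside the Safety Population (Protocol 17.1.2, SAP 2.1.1.1) and the Full Analysis Set (Protocol 17.1.1, SAP 2.1.1.2), both of which require study drug to have been given. This path is plausible, since section 15.1 lists the start of invasive ventilation as a reason to discontinue study drug.
- *Recovers, then dosed.* Nothing worsens after dosing, so there is still no AE.
- *Dosed, then worsens or recurs more often.* The exception applies. The event becomes an AE, reportable if serious.
- *Same event at the Day 5 blood gas.* It is an AE whatever its cause (14.1) and, if serious, is reported whatever its relation to the drug (14.10.1).

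The same harm is thus handled differently according only to whether the first dose has been given.

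**Step 2: look for another record.**

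- Protocol 15.2: date and reason for withdrawal, including death, go in the eCRF, but only if the subject is withdrawn.
- Protocol 13.14: a concomitant therapy is entered with its start date and the reason for it.
- SAP 2.1.2.4: current medical conditions are listed for Randomized Patients, but the stated time point is screening.
- SAP 2.1.2.5 to 2.1.2.8: drugs and therapies are listed for Randomized Patients from screening to Day 14.
- SAP 2.1.2.11.1.1: the AE listing covers Randomized Patients, but its period begins at the start of treatment.
- Protocol 22.1: monitors check the eCRF against source documents, and the sponsor reviews cases as needed.

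These can leave a trace. None imposes the 24-hour report, and none asks whether a study procedure caused the event.

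**Step 3: causality.** Sections 14.6 and 14.8 record causality to the study drug only. Even the Day 5 event in Step 1 would have no structured field linking it to the blood gas.

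**Step 4: size.** The planned sample is 60 (section 18), with one pre-dose sampling each, so at most 60 × 1 = 60 samplings. The documents give no rate of serious harm. Taking an *assumed* rate *p* per sampling, the expected number is 60*p* and the chance of at least one event is 1 − (1 − *p*)^60:

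- *p* = 0.5%: 60 × 0.005 = 0.3 events; 1 − 0.995^60 = 26%
- *p* = 1%: 60 × 0.01 = 0.6 events; 1 − 0.99^60 = 45%
- *p* = 2%: 60 × 0.02 = 1.2 events; 1 − 0.98^60 = 70%
- *p* = 5%: 60 × 0.05 = 3.0 events; 1 − 0.95^60 = 95%

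These figures are upper limits for each assumed rate, because fewer than 60 subjects will be sampled with oxygen removed. Category 5 subjects need no oxygen. Section 13.10 lets the test be judged not possible. SAP 2.1.2.10.2.6 provides for tests done on oxygen or not done.

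**The case against.** The strongest defence has four parts.

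1. *Opening the AE window at first dose is a coherent choice for comparing drug safety.* This stands. It explains why pre-dose events should stay out of the comparative tables. It does not explain why harm from a study procedure should be classed as a pre-existing condition or lack an expedited report.
2. *Other records exist.* This also stands, as Step 2 shows. In addition, an emergency-deviation report under section 16.1 would arguably reach the sponsor, and section 16.2 obliges the sponsor to amend the protocol on important new information. These routes are slower and were not set up to catch procedure harm, but they rule out saying that such harm is never recorded or that the sponsor has no way to learn of it.
3. *The exposure is limited.* The feasibility judgement in 13.10 addresses patients on high flow or mask, and every subject has already had SpO₂ measured on room air at screening (sections 7.1 and 13.7). This reduces the expected number. It does not remove the gap, since screening data may be up to 7 days old at consent (section 13) and the duration off oxygen may differ.
4. *Moving the start date alone would not identify procedure harm*, because causality is recorded to the drug only. This is correct, and the fix below takes it in.

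**Conclusion.** The gap is real and is written into the rules. Between consent and first dose, harm caused by the required blood gas is not an AE and is not reported to the sponsor as an SAE within 24 hours, unless it worsens or its incidence increases after dosing. If the subject is never dosed, the event is also outside both analysis sets. The number exposed is at most 60, and lower with oxygen removed. Any event count rests on an assumed rate.

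Three stronger readings are tempting, and the documents do not support them:

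- *Such harm is never reported, or the subject disappears from all outputs.* The withdrawal reason, therapy entries, Randomized Patients listings and monitoring can all leave a trace.
- *All 60 subjects are sampled with oxygen removed.* Some need no oxygen, some may be sampled on oxygen, and some may not be sampled.
- *The treatment comparison is biased.* The events precede the drug in both arms, so neither the post-dose AE tables nor the power calculation is affected.

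The change is worth making for safety oversight. It does not bear on the primary analysis.

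**What to change.** - **Protocol 14.1 and 14.10.1:** add wording such as *From informed consent to the first dose, any untoward event judged to be caused by a procedure done for the study is recorded in the eCRF and, if serious, is reported to the sponsor within 24 hours.* State that this means procedures performed because the protocol schedules them, since blood gases may also be taken in routine care.
- **Protocol 14.1:** limit the sentence on current medical conditions to pre-dose events not caused by a study procedure.
- **Protocol 14.6 and 14.8:** add a yes/no item, related to study procedure, beside causality to the study drug. It then serves later blood gases as well.
- **SAP 2.1.2.11.1:** list the pre-dose procedure-related events separately for Randomized Patients. Leave the post-dose AE tables in the Safety Population as they are.

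The cost is protocol and eCRF wording, one listing, a few extra reports and one extra causality judgement. The blood gas procedure, dosing, sample size and comparative AE tables do not change.

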14.2 Definition of ADR

ADR is at least reasonably likely to be related to the study drug and a causal relationship cannot be ruled out (see "14.6 Causality").

14.3 Severity of AEs

The severity of an AE will be assessed by classifying the AE into three grades: mild, moderate, and severe, referring to the following criteria and Pharmaceutical Safety Notification No. 80 (June 29, 1992) "Criteria for Classification of Seriousness of Adverse Drug Reactions". Grades 1, 2, and 3 defined in the above mentioned notification correspond approximately to mild, moderate, severe, respectively.

■Criteria

- 1) Mild : Symptoms are mild and easily tolerated by the subject.
- 2) Moderate : The event causes the subject discomfort and interrupts the subject's usual activities and some treatment is required.
- 3) Severe : The event makes daily activities severely.

■Reference: Cited from Pharmaceutical Safety Notification No. 80 "Criteria for Classification of Seriousness of Adverse Drug Reactions"

Grade 1	The event considered to be a minor adverse drug reaction
Grade 2	The event considered to be neither a serious nor a minor adverse drug reaction
Grade 3	The event considered to be a serious adverse drug reaction. In other words, it may result in death or permanent dysfunction that interferes with daily life depending on the subject's nature and condition at the time of onset.

14.4 SAEs

The following AEs are defined as SAEs. Scheduled hospitalization for surgery or examination, educational hospitalization, hospitalization and prolongation of hospitalization due to the convenience of the home caregiver, hospitalization for disease control, and hospitalization for health care (medical examination) check will not be regarded as hospitalization and prolongation of the hospitalization.

- 1) Results in death.
- 2) Is life threatening.^{※1}
- 3) Hospitalized to hospital or clinic^{※2} or require prolongation of existing hospitalization for treatment.
- 4) May result in disability/incapability.
- 5) May likely result in disability/incapability.
- 6) Is serious according to items 1) through 5)^{※3} above.
- 7) Is a congenital anomaly/birth defect

※1 : The term "life threatening" refers to an event in which the subject was at risk of death at the time of the event; it does not refer to an event that hypothetically might have caused death if it was more severe.

※2 : "Hospitalization" in this clinical study refers to staying at a medical institution for at least one night. And prolonged treatment in an outpatient setting, such as infusion, or staying at a medical institution intended for examination will not be regarded as hospitalization. If a patient has been treated for a long time on the emergency visit, the investigators will judge whether the case is a hospitalization case or not, taking the situation into account.

※3 : In case of a significant event that does not result in immediate life-threatening or death or hospitalization but may jeopardize the subject or require intervention to avoid the consequences described above, whether expedited reporting, as described below, is required or not should be judged based on the medical and scientific reasons, however, it should usually be considered serious. For example, blood disorders, renal and hepatic disorders, and central nervous system disorders which are considered medically important, bronchospasm requiring intensive care in the emergency room, or convulsions that do not result in hospitalization, drug dependency or substance abuse, etc. are included in this criterion.

14.5 Significant AEs

A significant AE is not an SAE, but is judged to be of special interest due to its clinical significance. A non-SAE leading to study drug discontinuation will be regarded as a significant AE.

14.6 Causality

The causal relationship between AE and study drug will be assessed as follows. If an AE is applicable to 2), the AE will be regarded as an ADR.

- 1) Not related: The temporal sequence of the AE to the administration of the study drug is not reasonable, or there is another obvious cause including current disease at onset, other medicinal product, or environmental factors or others.
- 2) Related: Events other than those "not related"

14.7 Predictability of AEs

Of AEs (including ADRs previously reported to the MHLW), those of which nature, severity, or frequency, etc. cannot be predicted according to the Investigator's Brochure ²will be regarded as "unknown" and those which can be predicted will be regarded as "known".

14.8 Observation of AEs

The investigators shall observe the occurrence of AEs carefully through medical interview, medical examination, etc. from the start of study drug administration. If any AE is observed, appropriate measures should be taken, and the AE shall be followed up by the investigators until the AE disappears

or resolves as far as possible. However, if the investigators judge that further follow-up observation is not necessary and discontinue follow-up observation, or if the subject refuses it, the reason shall be entered in the eCRF.

For any AEs that have occurred, information of the name of the event, date and time of onset (or date and time when the event was found), severity, seriousness (serious/non-serious), action taken with the study drug (if yes, its contents), treatment for the event (yes or no), outcome, date and time of outcome (when the event disappeared, the date and time of disappearance), and causality to the study drug should be entered in detail in the eCRF.

14.9 Pregnancy

When a female subject has been known or suspected to be pregnant during the study period, the investigators shall immediately discontinue the study drug administration and shall report the prespecified information (at least subject identification code, date of acknowledgment of pregnancy, dates of start and discontinuation of the study drug administration) to the sponsor. Pregnancy is not handled as AE, but the follow-up observation shall be conducted until the outcome (delivery, etc.) is confirmed.

Data on sargramostim in pregnant and lactating women are limited, and there are no data on inhalation administration of sargramostim, thus the safety of sargramostim has not been established. Risks for spontaneous abortion and harm to the embryo and fetus have been reported in the rabbit studies.

There is no information on sargramostim regarding its presence in human breast milk, its effects on breastfeeding children, or its effects on milk production. It has been reported that administration of sargramostim to rabbits during lactation resulted in decreased survival of offspring after birth.

